#### **13.4 Demographics and baseline characteristics**

- 1) Descriptive statistics of demographic information and baseline characteristics (such as previous history of comorbidity and medication) will be presented;
- 2) Comparison of baseline numeric variables (such as age, etc.) between groups will be performed with independent sample t-test or Wilcoxon rank sum test. Comparison of categorical variables (such as gender, presence of a comorbidity, etc.) between groups will be performed with chi-square test or Fisher exact test. Information (e.g., p-values) will only be used in selecting covariates for later sensitivity (adjusted) analysis of the primary outcome.

#### **13.5 Effectiveness evaluation**

##### **Evaluation of primary endpoint**

The incidence of postoperative delirium within 5 days after surgery will be calculated. Comparison between groups will be performed with chi-square or Fisher's exact test. The relative risk and the corresponding 95% confidence interval (CI) will be calculated to measure the magnitude of difference in risk of having postoperative delirium between groups.

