### **4.2 Sample size calculation**

The incidence of postoperative delirium is about 14% in elderly patients who underwent laparoscopic surgery for colorectal cancer [Tei et al., 2016]. We assume that the incidence of postoperative delirium will be reduced by 1/3 in patients receiving EEG-guided care [Chan et al., 2013]. With a two-sided significance and power set at 0.05 and 80%, respectively, the sample size required to detect the reduction is 742 patients per group. Taking into account a loss-to-follow-up rate of about 5%, we plan to enroll 780 patients in each group.

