## **7. Data collection**

### **7.1 Preoperative data**

- 1) Determine patient's eligibility based on the inclusion and exclusion criteria;
- 2) Mini-mental Status Exam;
- 3) Demographic data, past medical and surgical history, medications taken at home and in hospital;
- 4) Electrocardiogram, echocardiogram if available;
- 5) Lab results.

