### **Sensitivity analysis**

In the ITT dataset, we will perform a sensitivity analysis by fitting a multivariable logistic regression model of the primary outcome with covariate adjustment. Prognostic or risk factors of postoperative delirium shown in previous literature, and baseline and perioperative variables that differed between groups ( $p < 0.10$ ) together with the intervention factor (administration of dexmedetomidine or not) will be entered into the regression model. As the incidence of delirium is not a rare event, the odds ratio (OR) estimate from the logistic regression analysis will possibly overestimate the relative risk (RR) – our measure of effect size in this study, we will convert the OR into RR using the Zhang and Yu method (Zhang J, Yu KF. What's the relative risk? A method of correcting the odds ratio in cohort studies of common outcomes. *Jama* 1998;280:1690-1)

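### The primary test is valid but unadjusted, and the only planned adjustment is a sensitivity model not fixed in advance; a prespecified adjusted primary analysis would add from about nothing to a few points of power

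*Combined protocol and SAP*

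**What the plan says.** Section 13.5 (Evaluation of primary endpoint) sets the primary test: "Comparison between groups will be performed with chi-square or Fisher's exact test". A relative risk with a 95% confidence interval is reported alongside. No covariate enters.

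Section 4.2 sizes the trial for that unadjusted comparison. The control rate rests on the statement that "The incidence of postoperative delirium is about 14% in elderly patients who underwent laparoscopic surgery for colorectal cancer". The effect is given as "We assume that the incidence of postoperative delirium will be reduced by 1/3 in patients receiving EEG-guided care", and the result is that "the sample size required to detect the reduction is 742 patients per group". Section 5.1 describes 1:1 randomisation and states no stratification factor.

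Possible predictors are collected before surgery. Section 7.1 lists demographic data, history and the "Mini-mental Status Exam". The case report form (CRF) has the Charlson index, the inclusion criteria cover ASA I to III, and the baseline table in Section F adds years of education. Section 1 names age as a risk factor for delirium.

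Adjustment is planned, but in a secondary role. Under Sensitivity analysis the plan says "we will perform a sensitivity analysis by fitting a multivariable logistic regression model of the primary outcome with covariate adjustment". That model takes risk factors from the literature (not listed) plus baseline and perioperative variables that differ between groups at p < 0.10. It names use of dexmedetomidine as the intervention factor and converts the odds ratio to a relative risk.

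**The concern.** Neither the randomisation nor the primary analysis uses any prognostic variable. In a trial sized at 80% power with no reserve, adjusting for preoperative predictors fixed in advance keeps the type I error, accounts for chance imbalance in those variables, and usually raises power.

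The sensitivity model does not fill this gap, for three reasons:
- Part of its covariate list depends on the data, because it is chosen by between-group p-values.
- Perioperative variables can arise after randomisation and may be changed by the intervention. Propofol dose is the obvious example, since the intervention works by adjusting propofol.
- The intervention factor it names is not the one under test here, which is EEG-guided care.

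If age or baseline cognition happened to be unbalanced, the plan would have no cleanly prespecified adjusted estimate to set beside the chi-square result.

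**Working it through.** **Inputs from section 4.2.** p1 = 0.14; p2 = 0.14 × 2/3 = 0.0933; two-sided alpha 0.05; power 80%; 742 per group; 780 enrolled per group for about 5% loss.

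**Input not in the documents.** R², the share of outcome variance explained by the preoperative covariates. It is assumed and varied below.

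**Step 1: reproduce the plan's figure.** With p̄ = 0.1167 and d = 0.0467,

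n = [1.960·√(2p̄(1−p̄)) + 0.842·√(p1(1−p1) + p2(1−p2))]² / d²

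= (1.960 × 0.4540 + 0.842 × 0.4528)² / 0.0467² = 742 per group.

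This matches. It is the uncorrected pooled formula; a continuity correction would give 784. Power at 742 is 80.0%. Enrolling 780 and losing 5% leaves 780 × 0.95 = 741, also 80.0%.

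**Step 2: approximate effect of adjustment.** Adjustment acts roughly like a sample of n / (1 − R²):

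| Assumed R² | Effective n per group | Power | Gain (points) |
|---|---|---|---|
| 0 | 742 | 80.0% | 0 |
| 0.01 | 749 | 80.4% | 0.4 |
| 0.03 | 765 | 81.2% | 1.2 |
| 0.05 | 781 | 82.0% | 2.0 |
| 0.10 | 824 | 84.0% | 4.0 |
| 0.15 | 873 | 86.0% | 6.0 |
| 0.20 | 928 | 88.0% | 8.0 |

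**Step 3: check by simulation.** There were 6,000 trials per scenario, 742 per arm, one normally distributed covariate, and an adjusted logistic Wald test against the unadjusted chi-square. The Monte Carlo standard error of each power is about √(0.8 × 0.2 / 6000) = 0.5 points.

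| AUC of covariate | R² | Unadjusted | Adjusted | Gain (points) |
|---|---|---|---|---|
| 0.58 | 0.01 | 80.7% | 80.5% | −0.2 |
| 0.64 | 0.03 | 80.4% | 81.4% | 1.0 |
| 0.69 | 0.06 | 80.4% | 82.0% | 1.6 |
| 0.73 | 0.09 | 80.2% | 82.8% | 2.6 |
| 0.78 | 0.15 | 80.7% | 86.1% | 5.4 |

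With no treatment effect, rejection was 4.8% to 5.6% unadjusted and 4.7% to 5.3% adjusted, so adjustment did not inflate the type I error.

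**Step 4: six covariates instead of one.** A further simulation at 742 per group gave changes of −0.4 points with no prognostic value, +0.4 (R² 0.01), +1.0 (0.03), +0.9 (0.06), +3.8 (0.11) and +7.3 (0.21). Useless covariates therefore cost almost nothing. The design assumptions imply 742 × (0.14 + 0.0933) = 173 events, ample for a list of about six.

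The simulated gains run at or somewhat below the Step 2 approximation, so that table is slightly generous.

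**The case against.** The strongest reply is that nothing is broken. The chi-square is prespecified and valid, estimates a marginal relative risk, matches the sample-size calculation and delivers the stated power. With no stratification factor stated, it ignores no design factor. All of this stands.

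A reader might go further than the documents allow in four ways:
- **That the predictors are strong.** No AUC, R² or odds ratio is given for any covariate. Section 1 names age as a risk factor without a strength. Section 3.2 removes dementia, stroke, Parkinson's disease and major depression, and the CRF also excludes MMSE of 23 or less, which narrows that predictor. (Section 3.2 has no such cut-off and the subgroup plan splits MMSE at 24, so the actual range is itself unclear.)
- **That a fixed amount of power is being lost.** The gain is conditional on R² and may be close to zero. The simulations also assume a correctly specified covariate effect, which favours adjustment.
- **That the change is free.** It needs no patients or data, but it needs a model, a standardisation step and a missing-covariate rule.
- **That the plan has no adjustment.** It does, and the literature risk factors enter whether or not they are unbalanced.

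The last point does not rescue the sensitivity model as a substitute, because its list is neither stated nor fixed and may include post-randomisation variables.

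**Conclusion.** The point holds as an efficiency and robustness improvement. It does not show that the primary test is wrong or that the trial falls short of its planned 80% power.

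At 742 per group and 14% against 9.33%, prespecified adjustment is worth about 0 points for weak predictors (R² about 0.01), about 1 to 4 points for R² of 0.03 to 0.10, and 5 or more only for R² of about 0.15 or higher (AUC near 0.78). For R² of 0.05 to 0.10, the approximation puts this at 781 − 742 = 39 to 824 − 742 = 82 extra patients per group. The arithmetic is secure; the predictive strength is an assumption. The case for the change rests on the asymmetry: a possible modest gain against a negligible loss if the covariates turn out to be uninformative.

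**What to change.** In section 13.5, make the primary analysis a logistic regression of delirium on randomised group plus a short fixed list of preoperative covariates, for example age, baseline MMSE, education, ASA class and Charlson score.

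- Report the marginal relative risk and risk difference by standardisation, with robust or bootstrap confidence intervals. This keeps the plan's effect measure and removes the need to convert an odds ratio.
- Include benign or malignant disease only if it is taken from the preoperative diagnosis in the study flow chart. The pathological diagnosis is recorded with the discharge information. The Charlson index on the CRF already scores malignancy, so the two overlap.
- Fix the list before any outcome data are seen by arm. Unblinding is not a clear deadline, because section 11 describes unmasking when an individual patient completes 30 days.
- State a simple rule for missing covariates.
- Keep the unadjusted chi-square or Fisher test as the sensitivity analysis.
- In the existing sensitivity model, drop selection by p-value and perioperative variables, and replace the dexmedetomidine reference with randomised group.

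The cost is SAP wording and a small amount of programming.

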### **Evaluation of secondary endpoints**

- 1) Non-normal continuous endpoints will be analyzed by the Wilcoxon rank sum test. The Hodge-Lehman method will be used to estimate median of between-group difference with 95% CI.
- 2) Time-to-event variables (length of ICU stay, length of hospital stay) will be analyzed by the Wilcoxon rank sum test or by survival analysis, with difference between groups assessed with Log-Rank test.
- 3) The incidence of postoperative complications and 30-day mortality will be compared with Chi-square test or Fisher's exact test as appropriate.

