## 8.2 Secondary outcomes

The secondary outcomes are as follows:

- 1) Incidence of emergence delirium;
- 2) Composite complication classified as Clavien-Dindo grade II or greater within postoperative 30 days;
- 3) 24-hour postoperative nausea and vomiting (PONV);
- 4) MMSE score change;
- 5) Length of hospital stay;
- 6) Intensive care unit (ICU) admission;
- 7) 30-day hospital readmission;
- 8) 30-day all-cause mortality

Postoperative complications are as follows:

- Myocardial ischemia or infarction
- Arrhythmia requiring treatment
- Circulatory insufficiency (requiring a vasopressor or inotropic agent infusion for more than 6 hours)
- Ischemic stroke
- Hemorrhagic stroke
- Acute lung injury
- Pulmonary embolism
- Pulmonary infection requiring antibiotic treatment
- Hypoxemia or respiratory insufficiency requiring supportive treatment including intubation, CPAP, BiPAP, high-flow (>10 L/min) face mask or nasal cannula for more than 6 hours
- Acute kidney injury requiring treatment
- Urinary tract infection requiring antibiotic treatment
- Ileus
- Sepsis
- Anastomotic leakage requiring treatment
- Urinary retention requiring treatment
- Pleural or intra-abdominal effusion requiring intervention
- Wound dehiscence requiring intervention
- Bowel obstruction requiring treatment
- Deep venous thrombosis requiring treatment
- Subcutaneous emphysema requiring treatment
- Surgical bleeding or hematoma requiring intervention
- Surgical site infection (superficial or deep, but not organ or space) requiring antibiotic treatment or procedural treatment (not at bedside)
- Surgical site infection (pelvic or intra-abdominal infection or abscess, i.e., organ or space) requiring antibiotic treatment or procedural treatment (not at bedside)

- Delayed emergence requiring treatment

The Clavien-Dindo Classification (<https://www.assessurgery.com/clavien-dindo-classification/>)

Grades	Definition
Grade I	Any deviation from the normal postoperative course without the need for pharmacological treatment or surgical, endoscopic and radiological interventions Allowed therapeutic regimens are: drugs as antiemetics, antipyretics, analgetics, diuretics and electrolytes and physiotherapy. This grade also includes wound infections opened at the bedside.
Grade II	Requiring pharmacological treatment with drugs other than such allowed for grade I complications. Blood transfusions and total parenteral nutrition are also included.

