**MMSE to be assessed within 48 hours before surgery and on POD 7 or before discharge.**

**Instructions: Score one point for each correct response within each question or activity.**

Patient name:			
Study sequence #:			
Date of surgery: 20__ - __ - __			
Date of the 1 st test: 20__ - __ - __; Date of the 2 nd test: 20__ - __ - __			
Maximum Score	Questions	Patient's Score	
		Pre-op	POD 5
5	“What is the year? Season? Date? Day? Month?”		
5	“Where are we now? State? County? Town/city? Hospital? Floor?”		
3	The examiner names three unrelated objects clearly and slowly, then the instructor asks the patient to name all three of them. The patient’s response is used for scoring. The examiner repeats them until patient learns all of them, if possible.		
5	“I would like you to count backward from 100 by sevens.” (93, 86, 79, 72, 65, ...) Alternative: “Spell WORLD backwards.” (D-L-R-O-W)		
3	“Earlier I told you the names of three things. Can you tell me what those were?”		
2	Show the patient two simple objects, such as a wristwatch and a pencil, and ask the patient to name them.		
1	“Repeat the phrase: ‘No ifs, ands, or buts.’”		
3	“Take the paper in your right hand, fold it in half, and put it on the floor.” (The examiner gives the patient a piece of blank paper.)		
1	“Please read this and do what it says.” (Written instruction is “Close your eyes.”)		
1	“Make up and write a sentence about anything.” (This sentence must contain a noun and a verb.)		
1	“Please copy this picture.” (The examiner gives the patient a blank piece of paper and asks him/her to draw the symbol below. All 10 angles must be present and two must intersect.)		
30	Total		

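### No analysis is named for MMSE change; the only route in the plan leaves baseline MMSE out as a covariate and reports a shift estimate too coarse for an integer score

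*Combined protocol and SAP*

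**What the plan says.** Section 8.2 lists "MMSE score change" as the fourth of eight secondary outcomes. Section 7.1 collects the preoperative score ("Mini-mental Status Exam"). Supplemental remark 2 gives the timing of the two tests ("MMSE to be assessed within 48 hours before surgery and on POD 7 or before discharge") and the scoring ("Score one point for each correct response within each question or activity"), so the total is an integer with a maximum of 30.

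Section 13.5, Evaluation of secondary endpoints, item 1, reads "Non-normal continuous endpoints will be analyzed by the Wilcoxon rank sum test", and then "The Hodge-Lehman method will be used to estimate median of between-group difference with 95% CI". No covariate is mentioned. Item 2 takes the lengths of stay, and item 3 takes complications and 30-day mortality. The remaining secondary outcomes are yes/no events. MMSE change is therefore the only one of the eight that item 1 can reach. The item does not name it, gives no rule for judging normality, and gives no method for a normally distributed endpoint.

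The only adjusted model is under Sensitivity analysis: "fitting a multivariable logistic regression model of the primary outcome with covariate adjustment". Section 13.4 says that the baseline comparisons "will only be used in selecting covariates for later sensitivity (adjusted) analysis of the primary outcome". Nothing in the plan conditions MMSE change on baseline MMSE. Section 13.1 places all secondary outcomes under a Benjamini-Hochberg procedure.

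**The concern.** Two features of the implied analysis look weak. First, each patient should have a preoperative MMSE, yet it enters only by subtraction. Conditioning on a baseline normally gives a more precise comparison than a change score. Second, differences of integer scores capped at 30 are heavily tied, and a Hodges-Lehmann shift computed on them tends to land on whole numbers. The trial could report a small p value beside a median difference of 0.

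At stake are the power and the readability of the only cognitive-score outcome among the eight secondary outcomes.

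**Working it through.** **Inputs.** From the documents: 742 per group, delirium 14% falling by one third (section 4.2), integer MMSE with maximum 30 (Supplemental remark 2). The documents give no MMSE mean, SD, pre-post correlation (rho) or effect size. All of those below are assumptions.

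**1. The plan's own figure.** With 14% against 14% x 2/3 = 9.33%, two-sided 0.05, 80% power and pooled variance without continuity correction, the sample size is 742 per group, as stated. It concerns delirium only and is used here as the arm size.

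**2. Precision, by algebra.** With equal variances, ANCOVA variance divided by mean-change variance = (1 - rho²) / [2(1 - rho)] = (1 + rho)/2.

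| rho | ratio | loss from using change | of 742 per arm |
|---|---|---|---|
| 0.3 | 0.65 | 35% | about 260 |
| 0.5 | 0.75 | 25% | about 186 |
| 0.7 | 0.85 | 15% | about 111 |
| 0.8 | 0.90 | 10% | about 74 |
| 0.9 | 0.95 | 5% | about 37 |

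This compares ANCOVA with a *mean* change-score analysis. It does not measure the loss against Wilcoxon, so simulation is needed.

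**3. Power, by simulation** (742 per arm, MMSE rounded and capped at 30; Wilcoxon on change against mean ANCOVA).

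| Assumed effect and distribution | rho 0.5 | rho 0.7 | rho 0.85 |
|---|---|---|---|
| Uniform 0.3-point shift, mean 27, SD 2.5 | 59% vs 69% | 79% vs 87% | 98% vs 99% |
| Uniform 0.3-point shift, mean 28, SD 2 | 74% vs 89% | 90% vs 96% | 100% vs 100% |
| Only delirious patients decline, by 4 points (14% vs 9.33%; baseline 24-30, mean 27.5, SD 2.2) | 25% vs 33% | 29% vs 45% | 37% vs 55% |
| Same, by 6 points | 33% vs 56% | 35% vs 60% | 37% vs 67% |
| 0.3-point shift, plus an extra exponential decline averaging 4 points in 8% of patients in both arms (baseline 24-30) | 63% vs 55% | 82% vs 67% | 97% vs 75% |

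The first two rows use 300 runs and the others 600. The simulation standard error is therefore at most √(0.25/300) = 2.9 and √(0.25/600) = 2.0 percentage points. Mean ANCOVA leads in the first four rows, apart from near-ties where power is close to 100%, and loses clearly in the last. A baseline-adjusted rank analysis matched or beat Wilcoxon on change, within simulation error, under a uniform shift, a delirium-driven decline and the skewed case. Its type I error was near 5%.

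**4. The Hodges-Lehmann estimate** (same uniform-shift model, mean/SD 27/2.5 and 28/2, rho 0.5 to 0.85).

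| True shift (points) | estimate exactly 0 |
|---|---|
| 0 to 0.3 | 98-100% of runs |
| 0.5 | 70-98% |
| 0.8 | 0-8% |
| 1.0 | 0-1% |

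The shift applies before rounding and capping, so the observed mean difference is somewhat smaller (about 0.26 for a shift of 0.3). At 0.3 points, SD 2.5 and rho 0.7, 79% of runs paired p<0.05 with an estimate of 0, and the 95% CI was [0, 0] in 72%.

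**5. What size of shift do the plan's figures suggest?** If MMSE falls only through delirium, the mean difference is (0.14 - 0.0933) x loss = 0.0467 x loss. A mean difference of 0.5 would need a loss of 0.5/0.0467 = 10.7 points per delirious patient. For losses of 2, 4 and 6 points, the simulated mean differences were 0.09, 0.18 and 0.28, and the Hodges-Lehmann estimate was exactly 0 in at least 99.7% of runs.

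**The case against.** The strongest reply is that the rank test is valid under randomisation, is reserved for non-normal data, and suits a bounded score. A mean-based model would also be debatable, and the choice is largely one of preference for one secondary outcome with no sample-size claim. Much of this stands. The last power row shows that replacing Wilcoxon with mean ANCOVA as the test could lose power. It does not answer the two remaining points: a baseline can be added without giving up ranks, and the planned effect estimate is poorly suited to integer scores.

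A reader might infer three stronger things that the documents do not support:

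- That the plan assigns MMSE to Wilcoxon outright and discards the baseline. The sentence is conditional on non-normality and MMSE is not named. A change score does use the baseline, though inefficiently.
- That the reported difference will be 0 whatever the truth. This holds for shifts below about half a point. The documents neither state nor exclude a larger one.
- That power is certainly lost. The direction and size depend on an unstated distribution.

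The baseline range is also uncertain. The case report form excludes MMSE of 23 or less, section 3.2 has no such cut-off, and the Subgroup analysis section plans a stratum below 24. The amount of ceiling and tying depends partly on which applies.

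**Conclusion.** The point holds as an efficiency and reporting weakness for one secondary outcome. The plan leaves the MMSE analysis unnamed, and its only available route does not condition on baseline. For rho of 0.5 to 0.9, a mean change-score analysis costs 25% down to 5% of the effective sample. The cost against Wilcoxon ranges from a clear loss to a reversal, depending on skew. The Hodges-Lehmann estimate would almost always be exactly 0 for a true shift below about half a point. Effects of that size are what the plan's delirium assumptions suggest if cognition declines mainly through delirium, but that mechanism is an assumption.

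The planned test is not invalid, and neither the primary outcome nor the 742 per group is affected.

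**What to change.** In section 13.5, add an item that names the MMSE analysis:

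- **Test:** postoperative MMSE compared between arms with baseline MMSE as covariate, by a proportional-odds model or rank ANCOVA. Choose one in advance and state that its p value enters the Benjamini-Hochberg procedure.
- **Effect estimate:** the ANCOVA-adjusted mean difference with a robust 95% CI, in place of the Hodges-Lehmann shift.
- **Sensitivity:** Wilcoxon rank sum on change, as now implied.

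Reconcile the timing of the second MMSE. Supplemental remark 2 says "MMSE to be assessed within 48 hours before surgery and on POD 7 or before discharge", but the score column on the same form is headed POD 5, and the study flow chart schedules no postoperative MMSE. Until these agree, the postoperative score is not fully defined.

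The cost is a short addition to the SAP and one extra model; baseline MMSE is already collected. The test and the mean difference answer slightly different questions and may disagree under strong skew, so the text should say in advance which one governs significance.
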